2.2.3 Preliminary Data

The proposed study builds upon the successful Jefferson/CIP research collaboration and the work completed through a prior Merck MISP-funded project. That project was a single group observational cohort study

testing the effect of the Pharmacists' Pneumonia Prevention Program (PPPP) on participant's vaccination knowledge, beliefs, and activation. In addition, as described above, an economic analysis was conducted to measure PPPP's intervention costs and to identify opportunities for increasing its efficiency.

[figure not shown]
PPPP was delivered to **203 older adults at predominantly African American senior centers and other community based venues** in
Philadelphia eight times in 2014, and consisted of: 1) a pharmacist-delivered
30 minute formal presentation, 2) a 10 minute culturally-sensitive live skit
performed by senior center actors, 3) small group action planning facilitated
by pharmacists, and 4) optional pneumococcal vaccination. Participants'
pneumonia and vaccination knowledge, beliefs, and activation were
measured at baseline, post-test, and 3 months.

Findings indicated that **PPPP significantly improved knowledge** of pneumococcal disease and immunization in an older, minority population using a novel senior center model of care. Specifically, there was a 54% increase in the total mean knowledge score among participants from baseline to 3 months. These findings are important because understanding pneumococcal disease and vaccination importance have consistently been linked to receipt of the vaccine ²⁰⁻²⁶

In addition, an increase in activation was observed among PPPP participants. More than one-third of participants who had not received the vaccination or had an unknown vaccination status at the start of the program stated that they received the vaccination as a result of PPPP participation. Participants also reported taking other activation steps including speaking with physicians and pharmacists about pneumococcal disease and vaccination as well as engaging in conversations with family members and friends about the topic.

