2.7.2 Definitions of Study Measures

Study measures will be assessed at baseline, immediately following the program ("posttest"), and 1 month after the program. The baseline and posttests will be administered in person on the date of the intervention. The 1 month follow up will be administered by phone (with up to 4 attempts to reach the participant). It should be noted that the team considered a more distal follow up point (i.e., at 2 or 3 months), but based on experience with the prior PPPP study felt that an earlier follow up would make it easier to reach participants with fewer call attempts. If the reviewers of this proposal conclude that 1 month is too soon for a follow up, we are willing to revise our plan to include a follow up at 2 or 3 months.

Knowledge and awareness of vaccine-preventable disease (Objective 1):

Knowledge and awareness about the target vaccine-preventable diseases will be assessed with a 15-20 item inventory encompassing the following domains: susceptibility to infection, symptoms of disease, severity of illness, and vaccination with an emphasis on vaccine efficacy, safety, and eligibility. These items will be selected following a review of the literature since no single validated instrument exists to assess knowledge of all three target diseases. ^{28,29,32,33,36-40}

Similar to the prior pneumonia project, **pneumonia knowledge** will be assessed using an instrument developed by our group using previously published literature. The prior instrument consisted of 6 "check all that apply" questions. Each item correctly checked was worth 1 point, for a maximum possible score of 28 points (see Figure 4 for a summary). We plan to retain the same instrument for the proposed study in order to enable comparison of pneumonia knowledge between the studies. However, we will also add a module pertaining to **zoster knowledge** which takes the same form as the established instrument.

Figure 4. Summary of Pneumonia Knowledge Instrument

Knowledge Assessment Questions	Maximum Number of Correct Responses Possible
Who is at risk of getting pneumonia?	9
How can you catch pneumonia from an infected person who is near you?	4
Which of these are symptoms of pneumococcal disease?	5

I should call my doctor or get emergency help if I get any of the following problems after vaccination:	5
Which of the following are possible side effects of the pneumonia vaccine?	5
TOTAL SCORE	28

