2.7.3 Sample Size Justification

The sample size was calculated using G*Power 3.0.10 and is based on the primary outcome measure (difference between change in mean knowledge score from baseline to 1 month for PHARM vs PEER). We plan to use a two-tailed independent samples t-test with α =0.05 to determine the between-group difference in mean knowledge scores at each timepoint. We seek to examine the difference, if any, in the effectiveness of the two approaches, PHARM and PEER; specifically, we wish to determine if the two approaches have similar results to within 20% difference expecting large variability (50% standard deviation). This difference is detectable at a power of 0.8 with 121 participants in each arm of the study. To ensure an adequate sample size, we scaled up the sample size calculation using the attrition rate from the prior pneumonia project. Attrition rate in PPPP was $\frac{203-143}{203}$ =0.296 ≈30%; thus scaling up by 30% yields a total sample size of 316 (158 in each arm).

As a secondary outcome, consistent with the prior pneumonia project, we plan to use a two-tailed paired samples t-test to determine the within-group difference in mean knowledge score between timepoints. However, because within-group differences are easier to detect than between-group differences, the sample size is powered to detect the 20% between-group difference.

2.8 Specific Drug Supply Requirements	None – vaccination is not included as a component of this study.	
2.9 Adverse Experience Reporting	Not required since vaccination is not being offered through this study.	
2.10 Itemized Study Budget	Provided as attachment.	

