TITLE: Randomized Trial of Peer-to-Peer Versus Pharmacist Education to

Improve Older Adults' Vaccination Knowledge Through the Senior Center Model of Care

CLINICALTRIALS.GOV

NCT NUMBER

NCT03239665

March 6, 2020 **DOCUMENT DATE:**

Overview of Statistical Analysis

The design of the study was a randomized trial with randomization to PHARM or PEER performed at the program date level. The primary outcome measure was a between-group comparison of change in knowledge for PHARM vs. PEER at BL vs. PT, and BL vs. M1. Secondary measures included between-group examinations of beliefs, trust, and activation at all 3 time points (BL vs. PT and M1). We also measured within-group differences in knowledge, beliefs, and activation and the intervention costs of PHARM and PEER, including program development, training and implementation.

Study data was recorded using paper forms and input into SAS Version 9.4 for analysis. Electronic data was password-protected by CIP while enrollment and data collection were ongoing. Files were checked to ensure de-identification prior to sharing with the Rutgers University investigators who completed the analyses.

Analysis was performed using an Intention-to-Treat (ITT) sample. This sample included all participants meeting study including criteria with ≥ 1 documented response from the baseline survey. In the case of missing data from the post-intervention or one-month follow-up survey, the matrix below was used to carry forward observations. For all tests, the significance level was chosen as $\alpha = 0.05$, and was downward adjusted via the Bonferroni method when appropriate.

Table 1. ITT approach for handling missing follow-up data.

BL Data	PT Data	M1 Data
Present	Present	Absent Utilize PT Data
Present	Absent	Present
	Utilize BL Data	
Present	Absent	Absent
	Utilize BL Data	Utilize BL Data

^{*}BL = baseline, PT = post-intervention, M1 = one-month follow-up

Baseline Demographics

Demographic analysis was carried out via t-test for continuous variables and Chi-square test for categorical variables.

Knowledge

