The number of correct responses to the knowledge items at each timepoint was calculated as a whole and by disease (pneumonia, influenza, zoster). Baseline knowledge was compared by race via Kruskal-Wallis test. Because the knowledge data were expected to be non-normal and integer-valued, knowledge items were assessed using nonparametric methods. Specifically, between-group differences in knowledge were assessed at each timepoint via Wilcoxon Rank-Sum test. Similarly, between-group knowledge differences across timepoints were assessed pairwise via Wilcoxon Rank-Sum tests with Bonferroni-corrected significance threshold of

 α =0.05/3=0.0167. Within-group differences in knowledge score across timepoints were tested pairwise using Wilcoxon Signed-Rank tests.

Beliefs

The percentage of respondents answering "Completely Agree" to each item at each timepoint was calculated and compared between PHARM and PEER, as in our PPPP study. Pairwise Wilcoxon Signed-Rank tests were run comparing within-group changes in beliefs across timepoints applying Bonferroni correction (α =0.05/3=0.0167). Either Chi-Square or Fisher's Exact tests were used to compare beliefs between groups at each timepoint, depending on expected cell counts.

Activation

For all participants, Chi-Square or Fisher's Exact testing was performed as appropriate at each timepoint to assess between-group differences in proportions of participants planning actions, including planning vaccination and planning to speak with a doctor, pharmacist, or family/friends, as well as actions taken, including vaccinations obtained and having spoken with a doctor, pharmacist, or family/friends.

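### Missing 1-month knowledge scores are filled with the same-day post-test or baseline score and no other missing-data analysis is planned, so the primary 1-month arm comparison can be biased in either direction

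*SAP*

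**What the plan says.** The SAP (Overview of Statistical Analysis) defines the primary outcome as a "between-group comparison of change in knowledge for PHARM vs. PEER at BL vs. PT, and BL vs. M1". The protocol's sample size section (2.7.3) rests on the change from baseline to 1 month alone.

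The analysis set is every eligible participant with at least one baseline response. For missing follow-up the SAP states: "In the case of missing data from the post-intervention or one-month follow-up survey, the matrix below was used to carry forward observations". Table 1 has three rows:

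- M1 missing, PT present: M1 takes the PT score ("Absent Utilize PT Data").
- PT missing, M1 present: PT takes the BL score.
- Both missing: both take the BL score.

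On timing, protocol section 2.7.2 says "The baseline and posttests will be administered in person on the date of the intervention". M1 is a telephone survey one month later, with at most four call attempts. The sample size was "scaled up the sample size calculation using the attrition rate from the prior pneumonia project", about 30%.

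Neither document mentions a complete-case analysis, multiple imputation, a likelihood-based model, a comparison of those reached with those not reached, or any sensitivity analysis for missing data.

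**The concern.** A PT score carries no information about retention, because it is taken within hours of the teaching. Using it as the M1 score assumes that people who could not be reached by phone forgot nothing. Using BL assumes that they gained exactly nothing. The two errors act in opposite directions, and which one dominates depends on how many people also lack PT.

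For the arm comparison, PT fill mixes the same-day difference into the 1-month difference. If the arms match on the day and diverge later, the filled difference is pulled towards zero. That matters here because the primary hypothesis (protocol 2.1.1) is that the two programmes give similar gains. If the arms differ on the day and converge later, the filled difference is too large. If one arm loses more people to follow-up and knowledge fades, a gap appears where none exists. With only one analysis planned, a reader cannot tell which case applies.

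The BL-to-PT comparison is probably little affected, since both measurements are taken in person on one day.

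**Working it through.** **Inputs from the documents.** Attrition in the earlier PPPP study, from protocol 2.7.3: p = (203 − 143)/203 = 60/203 = 0.2956, which reproduces the stated 30%. Participants per arm: 121 × 1.30 = 157.3, rounded up to the stated 158. Planned difference 20 and SD 50, both in per cent. Rank-sum test at 0.05/3 = 0.0167 (SAP, Knowledge). At the planning rate, 158 × 0.2956 ≈ 47 people per arm would enter the 1-month test with a filled score.

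**Assumptions not in the documents.** Missingness at random and equal between arms unless stated, PT always present unless stated, correlation 0.6 between the BL-to-PT and BL-to-M1 changes, SD 50 applied to change scores, and no clustering by programme date.

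**Step 1: arm difference under PT fill.** Let dPT and dM1 be the true arm differences in change at PT and M1. Then

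filled difference = (1 − p) × dM1 + p × dPT.

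For 0 at PT and 20 at M1: 0.7044 × 20 + 0.2956 × 0 = 14.1. The other rows follow in the same way. Rejection rates come from 4,000 simulated trials per row at p = 0.2956.

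| True dPT / dM1 | Filled difference, p = 0.2956 | Filled difference, p = 0.15 | Rejection, carry-forward | Rejection, observed M1 only |
|---|---|---|---|---|
| 0 / 20 | 14.1 | 17.0 | 0.52 | 0.68 |
| 20 / 20 | 20.0 | 20.0 | 0.83 | 0.67 |
| 20 / 10 | 13.0 | 11.5 | 0.41 | 0.17 |
| 20 / 0 | 5.9 | 3.0 | 0.07 | 0.018 |

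The simulated mean differences agree with the formula to within about 0.2. Repeat simulations move the carry-forward rejection rates by a few hundredths, partly because they depend on the average amount of fading assumed. In the second row carry-forward is unbiased and has more power. In the last row the true 1-month difference is zero, so 0.07 is a false rejection rate against a nominal 0.0167.

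**Step 2: unequal loss, no true difference.** If a fraction f of the PT gain G is lost by M1 in both arms,

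false gap = (difference in missing fraction) × f × G.

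With 20% v 40% missing and f = 0.40: 0.20 × 0.40 = 0.08 of G. If G were 54 this is 0.08 × 54 = 4.3 points (4.4 simulated), with false rejection 0.05. With 10% v 20% missing: 0.10 × 0.40 = 0.04 of G. The value 54 is borrowed from PPPP's 3-month gain only to set a scale. The documents give no PT gain.

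**Step 3: within-arm retention.** Let r be the true fraction of the PT gain retained at M1, and q the share of those missing M1 who also lack PT. Then

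apparent retention = (1 − p) × r + p × (1 − q).

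- r = 0.8, q = 0: 0.7044 × 0.8 + 0.2956 = 0.859.
- r = 0.8, q = 0.25: 0.5635 + 0.2956 × 0.75 = 0.785.

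So a true 80% is reported as 86% or as 78.5%. The two errors cancel when q = 1 − r.

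**Step 4: standard error.** In the 0/20 case the nominal and empirical standard errors of the filled difference are 5.67 and 5.72. The defect is bias, not a wrong standard error.

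**Step 5: the alternative.** Multiple imputation within arm (normal model, 20 imputations, pooled t test, 3,000 trials, p = 0.2956) gives estimates of 20.1, 19.8 and 0.1 for 0/20, 20/20 and 20/0, with rejection rates of 0.77, 0.76 and 0.015. With 20% v 40% missing and no true difference it gives 0.03 (rejection 0.019).

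**The case against.** **The bias is conditional and the documents supply none of the conditions.** If missingness and fading are equal in the two arms and PT is present, the bias is zero. The protocol reports fading for trust, not for knowledge. PPPP was "measured at baseline, post-test, and 3 months" and found a 54% knowledge gain at 3 months, but with no PT value given, decay cannot be derived. This stands: the figures are illustrations. It does not remove the need for a second analysis, because the plan offers no way to find out.

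**The cases are extreme and the attrition rate is high.** A full 20-point difference appearing or vanishing within a month is a strong assumption. The 29.6% comes from a 3-month follow-up, and the investigators chose 1 month because they "felt that an earlier follow up would make it easier to reach participants with fewer call attempts". This also stands in part. At 15% loss, the 20/10 case is off by only about 1.5 points, but the 0/20 case still loses 3.

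**The rejection rates ignore clustering.** Randomization was by programme date, and PHARM may have only 3 to 6 groups. With an assumed 3 PHARM and 6 PEER dates and no true difference, false rejection on observed M1 data was 0.03, 0.05 and 0.12 at intraclass correlations of 0.01, 0.02 and 0.05. The rates above therefore isolate the missing-data effect and do not predict this trial's error rates. Clustering is a separate defect and does not cure this one.

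**Replacing the primary method is post hoc.** The SAP is dated March 2020 and written in the past tense, and a sensitivity analysis might seem enough. But the missing value itself should be handled by a defensible rule, and keeping the Table 1 result alongside lets readers see what the change does.

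**Conclusion.** The concern holds. A primary 1-month comparison rests on one untested fill rule, under which the same-day score stands in for retention. The bias can have either sign. At 29.6% loss it is about 6 points against a planned difference of 20 when the arm difference appears or disappears entirely after PT. It is about 3 points in those cases at 15% loss, and zero when the arm difference is constant and loss is equal. Unequal loss of 20% v 40%, with 40% of the gain forgotten, gives a false gap of 8% of the PT gain.

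That the plan uses carry-forward and nothing else is certain from the text. The size of the effect rests on assumed decay, attrition by arm and correlation. This should be changed, but it does not invalidate the trial: BL-to-PT is largely unaffected and the remedy uses data already collected.

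**What to change.** For the primary BL-to-M1 comparison, replace carry-forward with an analysis valid under missing-at-random.

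- **Preferred:** multiple imputation within arm from baseline and post-test scores, by predictive mean matching so that imputed scores stay integer and in range. This respects the SAP's reason for its choice of test ("Because the knowledge data were expected to be non-normal and integer-valued, knowledge items were assessed using nonparametric methods"). Keep the rank-based comparison in each imputed data set and pool the Mann-Whitney probability by Rubin's rules.
- **Alternative:** a repeated-measures mixed model on all observed scores. If programme date is modelled, use a small-sample correction, given the few PHARM groups.
- Report PT and M1 missingness by arm.
- Add a delta-adjusted sensitivity analysis that lets unreached participants differ from missing-at-random.
- Keep the Table 1 carry-forward result as a sensitivity analysis, and date and label the change.

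**Cost:** SAP wording, a re-run on existing data and somewhat more analysis work. Power falls in some cases: in the 20/20 scenario 0.76 with imputation against 0.83 with carry-forward at correlation 0.6, and about 0.69 if the correlation is 0.3. The power of 0.76 comes from the normal-model version in step 5. A check of the predictive mean matching version gave similar power to the normal model at correlation 0.6 (0.79 for both in that run). The result then depends on missing-at-random, which the delta-adjusted analysis is there to test.

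### The primary between-arm knowledge test is an unadjusted rank-sum test on change scores, and no knowledge analysis uses the baseline score as a covariate

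*SAP*

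**What the plan says.** The SAP overview states: "The primary outcome measure was a between-group comparison of change in knowledge for PHARM vs. PEER", from baseline (BL) to post-test (PT) and from baseline to one month (M1). Protocol section 2.7.3 bases the sample size on the "difference between change in mean knowledge score from baseline to 1 month for PHARM vs PEER".

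The SAP's Knowledge section gives two families of between-arm tests. In the first, "between-group differences in knowledge were assessed at each timepoint via Wilcoxon Rank-Sum test". In the second, "between-group knowledge differences across timepoints were assessed pairwise via Wilcoxon Rank-Sum tests", at a threshold of 0.05/3 = 0.0167. The second wording is terse. Read with the primary-outcome definition, it means a rank-sum test on pairwise change scores. Neither family includes a covariate, and the section describes tests only, with no effect estimate or confidence interval.

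Baseline knowledge is collected by design (Protocol section 2.7.2). The ITT sample requires at least one documented baseline response, which is less than a complete baseline knowledge score. The SAP describes "randomization to PHARM or PEER performed at the program date level", and Protocol section 2.5.1 plans PHARM as 3 groups of 50 to 55 or possibly 6 groups of 25 to 30.

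**The concern.** The primary hypothesis is that the two arms improve knowledge to a similar degree, so the result depends on a precise contrast that is not moved by where the arms happened to start. The two test families handle baseline in opposite ways. A single-timepoint comparison carries a share of any baseline gap forward. A change-score comparison removes too much of it, through regression to the mean. With the same data the two can point in different directions, and the SAP does not say how to reconcile them.

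Chance gaps are a practical risk here because few units are randomised. Participants who attend on the same date may resemble one another, so a handful of dates balances baseline knowledge less well than individual randomisation of 316 people. A gap could then create an apparent difference between arms or mask a real one.

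**Working it through.** **Inputs.** From Protocol section 2.7.3: difference 20%, SD 50% (0.4 SD), "two-tailed independent samples t-test with α =0.05", power 0.8, 121 per arm, 158 per arm enrolled. The text does not say whether the 50% is the SD of the change or of a single score. Not in the documents, so assumed: baseline-to-follow-up correlation ρ = 0.3 to 0.7, and intraclass correlation (ICC) of baseline score within date = 0.01 to 0.05.

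**The plan's own figure.** n per arm = 2 × (1.96 + 0.84)² / 0.4² gives 99 by normal approximation, or 100 with the t distribution. The stated 121 is not reproduced; it is conservative, with t-test power of 0.873. The step 121 × 1.30 = 157.3, rounded up to 158, does reproduce. The discrepancy is separate from this point.

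**Precision.** With equal score variance σ² at both times and n per arm, the variance of the arm difference, in units of 2σ²/n, is:

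- follow-up score alone: 1
- change score: 2(1 − ρ)
- baseline as covariate: 1 − ρ²

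The ratio of covariate-adjusted to change-score variance is (1 − ρ²) / [2(1 − ρ)] = (1 + ρ)/2.

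| ρ | adjusted / change | adjusted / follow-up only |
|---|---|---|
| 0.3 | 0.65 | 0.91 |
| 0.5 | 0.75 | 0.75 |
| 0.7 | 0.85 | 0.51 |

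If the 50% SD is that of the change, the required 99 per arm falls to 64, 74 or 84, and power at 121 rises from 0.875 (normal approximation) to 0.971, 0.949 or 0.921. If it is that of a single score, the change analysis needs 138, 99 or 59 per arm and the adjusted analysis 90, 74 or 51. All these figures ignore clustering by date.

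**Residual baseline gap.** In expectation under a linear model, a baseline difference D between arms leaves ρD in a single-timepoint contrast, −(1 − ρ)D in a change contrast, and 0 after covariate adjustment.

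With k dates of m participants per arm, the SE of D in single-score SD units is √{[2/(km)] × [1 + (m − 1) × ICC]}. Example for 3 dates of 53 and ICC 0.05: √{(2/159) × 3.60} = 0.213. Individual randomisation gives √(2/159) = 0.112. The number of PEER dates is not stated, so it is taken as equal to PHARM. Ten educators with 5 or 6 participants each would make 50 to 60 per date, which fits about three dates if all ten work each time.

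Size of the shift in the change contrast from a one-SE gap, (1 − ρ) × SE, in SD units:

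| Dates per arm | ICC | SE of D | ρ = 0.3 | ρ = 0.5 | ρ = 0.7 |
|---|---|---|---|---|---|
| 3 of 53 | 0.05 | 0.213 | 0.149 | 0.106 | 0.064 |
| 3 of 53 | 0.01 | 0.138 | 0.097 | 0.069 | 0.041 |
| 6 of 26 | 0.05 | 0.170 | 0.119 | 0.085 | 0.051 |
| 6 of 26 | 0.01 | 0.127 | 0.089 | 0.063 | 0.038 |

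The range is 0.038 to 0.149 SD, or 0.038/0.4 = 10% to 0.149/0.4 = 37% of the design difference if the 50% is a single-score SD. If it is the SD of the change, the fraction is √[(1 − ρ)/2] × SE / 0.4, which runs from 0.387 × 0.127/0.4 = 12% to 0.592 × 0.213/0.4 = 31%. For single-timepoint tests the same sizes apply with the ρ columns reversed and the opposite sign.

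**The case against.** The strongest reply is that a change-score comparison is legitimate. Under randomisation it is unbiased, a chance gap is part of its sampling error, and the SAP gives a reason for simple nonparametric tests: scores expected to be non-normal and integer-valued. This stands as far as validity goes. The extra variance and the residual gap are one phenomenon seen from two sides, so their sizes should not be added. But non-normality argues for a rank-based form of adjustment rather than for none.

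A reader who sees only the sentence on tests at each timepoint might infer that the primary analysis ignores baseline altogether. The documents do not support that: both define the primary outcome as change, so baseline enters by subtraction. Only the per-timepoint tests leave it out.

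A reader might also take one figure, such as a shift of a quarter of the design difference, as the size of the problem. That needs ρ = 0.5, ICC = 0.05 and the three-date layout together. None of these is fixed by the documents, so only the range is defensible.

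Three further objections stand and shape the fix. One baseline response does not guarantee a usable baseline score. Adjusting for individual baseline removes a between-date gap in full only if the slope between dates equals the slope within dates. With few dates, ordinary mixed-model or robust standard errors are unreliable.

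**Conclusion.** The point holds as one of efficiency and robustness. The primary comparison is an unadjusted rank-sum test on change, accompanied by unadjusted tests at each timepoint, and no knowledge analysis uses the collected baseline score as a covariate. Adjustment would reduce the variance to 0.65 to 0.85 of its change-score value for ρ between 0.3 and 0.7, under a linear model without clustering; carried over to rank tests, that figure is a guide only. A one-SE baseline gap could move the change contrast by about 0.04 to 0.15 SD against 0.4 SD, given ICC 0.01 to 0.05 and equal numbers of dates in the two arms.

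Two stronger conclusions that a reader might draw are not supported. The documents do not show that the primary result is biased, only that it is more exposed to chance imbalance than it need be. Nor does baseline adjustment repair the analysis of date-randomised participants as if they were independent. That is a separate and probably larger issue, as is the carry-forward of missing follow-up scores.

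**What to change.** Amend the SAP's Knowledge section as follows.

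- Compare the M1 score, and separately the PT score, between arms with the baseline knowledge score as covariate. Use a rank-based covariance analysis for the test, and report a baseline-adjusted mean difference with 95% CI.
- State a rule for incomplete baseline scores: how an unanswered item counts, and how a missing total is filled in without reference to arm.
- Take inference at program-date level with a small-sample method, such as a permutation test over dates. Check first that the number of dates allows it. With 3 dates per arm there are 20 allocations, so the smallest two-sided p-value is 2/20 = 0.10, and a t-based analysis of date-level summaries would be needed. With 6 per arm there are 924, and the floor is 2/924 = 0.002.
- Keep the existing rank-sum tests as sensitivity analyses.

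The cost is a few lines of SAP text and code, with no new data or participants. Accounting for dates may widen the interval by more than baseline adjustment narrows it, and the report should say so. The SAP is dated March 2020 and written in the past tense; if results are already known, the adjusted analysis should be labelled as added post hoc and should not replace the stated primary test.
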